Clinical Study Protocol				
Drug Substance	Esomeprazole 20 mg/ASA 81 mg			
Study Code	D961FC00010			
Edition Number	1			
Date				

An Open-label, Randomized, Single-center, 2-way Cross-over Interaction Study, Evaluating the Effect of Esomeprazole 20 mg/Acetylsalicylic acid 81 mg on the Pharmacodynamics and the Pharmacokinetics of Clopidogrel on Days 1 and 9 in Healthy Volunteers

S	n	o	n	S	o	r	•

AstraZeneca AB, [name]

The following Amendment(s) and Administrative Changes have been made to this protocol since the date of preparation:

Amendment No.

Date of Amendment

Local Amendment No:

Date of Local Amendment

Administrative
Change No.

Date of Administrative
Change No.

Date of Local Administrative
Change No.

Date of Local Administrative
Change No.

This submission /document contains trade secrets and confidential commercial information, disclosure of which is prohibited without providing advance notice to AstraZeneca and opportunity to object.

PROTOCOL SYNOPSIS

An Open-label, Randomized, Single-center, 2-way Cross-over Interaction Study, Evaluating the Effect of Esomeprazole 20 mg/Acetylsalicylic acid 81 mg on the Pharmacodynamics and the Pharmacokinetics of Clopidogrel on Days 1 and 9 in Healthy Volunteers

Principal Investigator

Study center(s) and number of subjects planned

This is a single-center study. Fifty-nine (59) healthy male and female volunteers will be enrolled and randomized to treatment.

Study period		Phase of development
Estimated date of first healthy volunteer enrolled	Q1 2011	Phase I
Estimated date of last healthy volunteer completed	Q3 2011	

Objectives

Primary objective

To assess the effect of esomeprazole 20 mg/acetylsalicylic acid 81 mg on the pharmacodynamics of clopidogrel by assessing maximal inhibition of platelet aggregation after 9 days of clopidogrel treatment relative to baseline

Secondary objectives

To assess the effect of esomeprazole 20 mg/acetylsalicylic acid 81 mg on the pharmacokinetics of the active metabolite of clopidogrel by assessing AUC, AUC_{0-last} and C_{ss.max} of the active metabolite of clopidogrel on Day 9

• To assess the safety and tolerability of clopidogrel given alone and concomitantly with esomeprazole 20 mg/acetylsalicylic acid 81 mg by assessing adverse events, vital signs, laboratory variables, electrocardiogram and physical examination

Exploratory objective

To summarize the pharmacodynamic and pharmacokinetic variables in relation to CYP2C19 genotype

Study design

This is a single-center, open-label, randomized, 2-way cross-over study designed to assess the pharmacodynamic and pharmacokinetic interaction between clopidogrel and esomeprazole 20 mg/acetylsalicylic acid 81 mg.

Target subject population

Healthy males, aged between 18 and 45 years inclusive, and females, aged between 18 and 55 years inclusive, with a body mass index between 19 and 30 kg/m² inclusive

Investigational product, dosage and mode of administration

Each healthy volunteer will receive oral administration of 2 treatments in randomized order:

- Treatment A: clopidogrel tablet 75 mg once daily for 9 days
- Treatment B: clopidogrel tablet 75 mg once daily for 4 days followed by esomeprazole 20 mg/acetylsalicylic acid 81 mg with clopidogrel tablet 75 mg once daily for 5 days

Comparator, dosage and mode of administration

None

Duration of treatment

The total study duration for each healthy volunteer is approximately 2.5 months. This includes a pre-entry visit within 28 days prior to randomization, 2 treatment periods of 9 days, washout periods of at least 14 days between the treatment periods (ie, between the last dose in period 1 and the first dose in period 2) and a follow-up visit 7 to 10 days after the last dose.

Outcome variable(s):

Pharmacodynamics

The primary variable is maximal inhibition of platelet aggregation which will be based on maximum platelet aggregation to $20 \mu mol/L$ adenosine diphosphate assessed at baseline (Day -1 for Period 1 and pre-dose on Day 1 in Period 2) and 24 h after dose on Day 9.

Pharmacokinetics

Area under the plasma concentration-time curve from time zero to infinity (AUC, primary variable), Area under the plasma concentration-time curve from time zero to time of last quantifiable concentration (AUC_{0-last}, primary variable), maximum steady state concentration in plasma ($C_{ss,max}$, primary variable) and time to reach maximum concentration (t_{max}) of the active metabolite of clopidogrel after dose on Day 9

Safety

Adverse events, vital signs, clinical laboratory variables, electrocardiogram, physical examination

Statistical methods

The pharmacokinetic variables and maximal inhibition of platelet aggregation will be analyzed using linear mixed models (1 for each variable) with fixed effects for period and treatment and a random effect for subject within sequence. The mean differences between the treatments in the maximal inhibition of platelet aggregation model will be calculated with 95% confidence interval for the differences. The ratio ((esomeprazole 20 mg/acetylsalicylic acid 81 mg + clopidogrel)/clopidogrel) of AUC, AUC_{0-last} and C_{ss,max} with corresponding 90% CI for the ratios will be calculated.

Subpopulation analysis by genotype may be performed if found necessary and if data allows.

Safety data will be presented with descriptive statistics.

TABLE OF CONTENTS

PAGE

	TITLE PAGE	1
	PROTOCOL SYNOPSIS	2
	TABLE OF CONTENTS	5
	LIST OF ABBREVIATIONS AND DEFINITION OF TERMS	9
1.	INTRODUCTION	12
1.1	Background	12
1.2	Rationale for conducting this study	12
1.3	Benefit/risk and ethical assessment	13
2.	STUDY OBJECTIVES	13
2.1	Primary objective	13
2.2	Secondary objectives	14
2.3	Exploratory objective	14
3.	STUDY PLAN AND PROCEDURES	14
3.1	Overall study design and flow chart	14
3.2	Rationale for study design, doses and control groups	17
4.	SUBJECT SELECTION CRITERIA	18
4.1	Inclusion criteria	18
4.2	Exclusion criteria	19
5.	STUDY CONDUCT	21
5.1	Restrictions during the study	21
5.2 5.2.1	Subject enrolment and randomization. Procedures for randomization	
5.3	Procedures for handling subjects incorrectly enrolled or randomized or initiated on investigational product	23
5.4	Blinding and procedures for unblinding the study (Not applicable)	
5.5	Treatments	
5.5.1	Identity of investigational product(s)	
5.5.2 5.5.3	Doses and treatment regimens	24 25

5.5.4	Storage	25
5.6	Concomitant and post-study treatment(s)	25
5.7	Treatment compliance	25
5.7.1	Accountability	
5.8	Withdrawal from study	26
5.8.1	Procedures for discontinuation of a subject from the study	26
6.	COLLECTION OF STUDY VARIABLES	26
6.1	Recording of data	26
6.2	Data collection and enrolment	27
6.2.1	Follow-up procedures	27
6.3	Safety	28
6.3.1	Definition of adverse events	
6.3.2	Definitions of serious adverse event	
6.3.3	Recording of adverse events	
6.3.4 6.3.5	Reporting of serious adverse events	
6.3.6	Physical examination	
6.3.7	ECG	
6.3.8	Vital signs	
6.4	Pharmacokinetics	33
6.4.1	Collection of samples	33
6.4.2	Determination of drug concentration	33
6.5	Pharmacodynamics	
6.5.1	Collection of samples.	

Appendix B

Additional Safety Information

LIST OF ABBREVIATIONS AND DEFINITION OF TERMS

The following abbreviations and special terms are used in this study Clinical Study Protocol (CSP).

Abbreviation or special term	Explanation
ADP	Adenosine diphosphate
AE	Adverse event (see definition in Section 6.3.1)
AMC	Active metabolite of clopidogrel
APTT	Activated partial thromboplastin time
ASA	Acetylsalicylic acid
AUC	Area under the plasma concentration-time curve from time zero to infinity
$\mathrm{AUC}_{0\text{-last}}$	Area under the plasma concentration-time curve from time zero to time of last quantifiable concentration
В	Blood (eg, B-Hb)
BP	Blood pressure
CI	Confidence interval
CPA	Clinical Pharmacology Alliance
CRF	Case report form (electronic/paper (eCRF/pCRF))
CSA	Clinical Study Agreement
CSP	Clinical study protocol
CSR	Clinical study report
$C_{ss,max}$	Maximum steady state concentration in plasma
CV	Coefficient of variation
CYP	Cytochrome P450
DNA	Deoxyribonucleic acid
EC	Ethics Committee, synonymous to Institutional Review Board (IRB) and Independent Ethics Committee (IEC)
ECG	Electrocardiogram (paper (pECG))
F	Faeces (eg, F-Hb)
FSH	Follicle stimulating hormone
GCP	Good Clinical Practice
GI	Gastrointestinal
GMP	Good Manufacturing Practice

Abbreviation or special term	Explanation
НЬ	Haemoglobin
hCG	Human chorionic gonadotropin
HIV	Human immunodeficiency virus
HPLC	High-performance liquid chromatography
ICH	International Conference on Harmonisation
IP	Investigational product
IPA	Inhibition of platelet aggregation
IUD	Intrauterine device
LIMS	Laboratory Information Management System
LLOQ	Lower limit of quantification
Max	Maximum
MedDRA	Medical Dictionary for Regulatory Activities
Min	Minimum
mIPA	Maximal IPA
mPA	Maximal PA
MS	Mass spectrometry
NSAID	Non-steriodal anti-inflammatory drug
OAE	Other significant adverse event (see definition in Section 11.1.1)
od	Once daily
OTC	Over-the-counter
PA	Platelet aggregation
PD	Pharmacodynamic/pharmacodynamics
PI	Principal Investigator
PK	Pharmacokinetic/pharmacokinetics
PPI	Proton pump inhibitor
PR (PQ)	ECG interval measured from the onset of the P wave to the onset of the QRS complex
QRS	ECG interval measured from the onset of the QRS complex to the J point
QT	ECG interval measured from the onset of the QRS complex to the end of the T wave
QTcF	QT interval corrected for heart rate using Fridericia's formula
RR	The time between corresponding points on 2 consecutive R waves on ECG

Abbreviation or special term	Explanation
S	Serum (eg, S-Calcium)
SAE	Serious adverse event (see definition in Section 6.3.2).
SD	Standard deviation
SOP	Standard Operating Procedure
t_{max}	Time to reach maximum concentration
U	Urine (eg, U-Hb)
WI	Work Instruction

1. INTRODUCTION

1.1 Background

The proposed therapeutic indication for combination product of the proton pump inhibitor (PPI) esomeprazole and acetylsalicylic acid (ASA) is prevention of cardio- and cerebrovascular events in patients at risk of developing gastric and/or duodenal ulcers associated with ASA.

Esomeprazole is the S-enantiomer of the PPI omeprazole, and acts through inhibition of the proton pumping enzyme H⁺/K⁺-ATP-ase located in the parietal cells of the gastric oxyntic mucosa, thus preventing hydrochloric acid secretion to the gastric lumen. Esomeprazole for oral use is currently approved for a variety of acid-related conditions, including the prevention of gastric and duodenal ulcers associated with non-steroidal anti-inflammatory drug (NSAID) therapy. Esomeprazole was first approved for marketing in Sweden in 2000, and is now approved in 125 countries.

The clinical development program includes 2 studies (D9617C00011 and D961FC00003) that contributed efficacy data showing that esomeprazole at doses of 20 mg and 40 mg once daily (od) prevents peptic (gastric and/or duodenal) ulcers in patients on continuous low-dose ASA treatment (for prevention of cardio- and cerebrovascular events) at risk of developing peptic ulcers. Both studies were randomized, double-blind, 26-week studies evaluating the efficacy and safety of esomeprazole 20 mg od (Study D9617C00011) or 20 mg and 40 mg od (Study D961FC00003) compared with placebo in patients on continuous low-dose ASA treatment.

1.2 Rationale for conducting this study

Clopidogrel has proven its efficacy in reducing atherothrombotic events after percutan coronar intervention, a considerable interindividual variability in response has been reported. Clopidogrel is administered as an inactive prodrug requiring metabolization by the hepatic cytochrome P450 system for its antiplatelet activity. The formed active thiol metabolite of clopidogrel (AMC) irreversibly inhibits adenosine diphosphate (ADP) mediated platelet activation and aggregation by antagonizing the P2Y12-receptor. In the formation of the AMC, different cytochrome P450 (CYPs) (CYP1A2, CYP2B6, CYP2C19, CYP2C9 and CYP3A4) have been shown in vitro to be involved in 2 different oxidative steps; some contribute more than others (Kazui et al), but based on several large studies assessing the role of genetic variation in clopidogrel responsiveness (Mega et al 2009, Shuldiner et al 2009) the role of CYP2C19 seems to be of major importance. In vitro studies suggest that both omeprazole and esomeprazole have a potential to inhibit CYP2C19 and thus to inhibit the metabolism of drugs metabolized by CYP2C19 (Li et al 2004). Previous interaction studies between clopidogrel and omeprazole or esomeprazole showed inconsistent results (Cuiseet et al 2009, Furuta et al 2010, Gilard et al 2008, Jermano et al 2009, Lapuerta et al 2008, Moceri et al 2009, Sibbing et al 2009, Siller-Matula et al 2009, Zuern et al 2009). In a recent study referenced in the US Plavix[®] Prescribing Information

using omeprazole 80 mg as a tool/probe to inhibit CYP2C19 in healthy subjects, the formation of AMC decreased by 46%, indicating an inhibition of CYP2C19 by this dose of omeprazole. Some of the previous PD studies indicated a dose response relationship with the presence or absence of interaction (Lapuerta et al 2008). As the combination product esomeprazole/ASA is given in order to prevent cardio— and cerebrovascular events in patients at risk, it is important to clarify if there is any drug-drug interaction between esomeprazole 20 mg/ASA 81 mg and clopidogrel as clopidogrel is commonly used for the same purpose together with ASA.

Light transmission aggregometry is regarded as the gold standard and has been chosen for measuring platelet aggregation (PA). The absolute change in platelet reactivity when measured with light transmittance aggregometry induced by 20 μ mol/L ADP showed strong correlation with the C_{max} value of the AMC. In contrast, no significant association was observed between the C_{max} value of the AMC and inhibition of PA (IPA) using a lower concentration of 5 μ mol/L ADP, hence only the higher dose of ADP will be used (Bouman et al 2009).

The aim of this study is to assess whether there is a pharmacological interaction between esomeprazole 20 mg/ASA 81 mg and clopidogrel.

1.3 Benefit/risk and ethical assessment

Acetylsalicylic acid, esomeprazole and clopidogrel have been available for marketed use for several years. The safety profiles are well described in the package inserts for esomeprazole and clopidogrel, respectively, at the following links:

http://www1.astrazeneca-us.com/pi/Nexium.pdf (esomeprazole)

http://products.sanofi-aventis.us/PLAVIX/PLAVIX.html (clopidogrel)

This is a standard drug-drug interaction study. There will be no direct medical benefits to the healthy volunteers who participate.

Healthy volunteers will be administered clopidogrel, a platelet inhibitor that may increase the risk of bleeding. Healthy volunteers will be observed at the study unit during the treatment period when clopidogrel is administered with esomeprazole 20 mg/ASA 81 mg and safety will be monitored. Any minor or major bleeding events will be required to be reported by the healthy volunteers to the study personnel.

2. STUDY OBJECTIVES

2.1 Primary objective

To assess the effect of esomeprazole 20 mg/ASA 81 mg on the pharmacodynamics (PD) of clopidogrel by assessing maximal IPA (mIPA) after 9 days of clopidogrel treatment relative to baseline

2.2 Secondary objectives

- To assess the effect of esomeprazole 20 mg/ASA 81 mg on the pharmacokinetics (PK) of AMC by assessing AUC, AUC_{0-last} and C_{ss,max} of AMC on Day 9
- To assess the safety and tolerability of clopidogrel given alone and concomitantly with esomeprazole 20 mg/ASA 81 mg by assessing adverse events (AEs), vital signs, laboratory variables, electrocardiogram (ECG) and physical examination

2.3 Exploratory objective

To summarize the PD and PK variables in relation to CYP2C19 genotype

3. STUDY PLAN AND PROCEDURES

This CSP has been subject to a peer review according to AstraZeneca standard procedures.

[figure not shown]
3.1 Overall study design and flow chart

The study will be performed at Quintiles AB, Uppsala, Sweden. This is an open-label, randomized, 2-way cross-over study designed to assess the PD and PK interaction between clopidogrel and esomeprazole 20 mg/ASA 81 mg. Fifty-nine (59) healthy male and female volunteers will be enrolled and randomized to treatment.

The total study duration for each healthy volunteer is approximately 2.5 months. This includes a pre-entry visit within 28 days prior to randomization, 2 treatment periods of 9 days, washout periods of at least 14 days between the treatment periods (ie, between the last dose in period 1 and the first dose in period 2) and a follow-up visit 7 to 10 days after the last dose. See Figure 1.

In each treatment period, the healthy volunteers will arrive at the study unit on Day -1 and start treatment on Day 1. For treatment A, the healthy volunteers will take the subsequent doses on Days 2 to 8 at home and receive the dose on Day 9 at the study unit (they will return to the study unit in the evening of Day 8). For treatment B, the healthy volunteers will take the subsequent doses on Days 2 to 4 at home and they will return to the study unit to receive the doses on Days 5 to 9.

Figure 1 Study flow chart

- a Healthy volunteers will be administered the following treatments in randomized order (see Section 5.5.2) in Period 1 and 2:
 - Treatment A: clopidogrel 75 mg once daily for 9 days
 - Treatment B: clopidogrel 75 mg once daily for 4 days followed by esomeprazole 20 mg/ASA 81 mg with clopidogrel 75 mg once daily for 5 days
- b Investigational product (IP, esomeprazole 20 mg/ASA 81 mg and clopidogrel)
- c The washout period will be at least 14 days between the last dose in period 1 and the first dose in period 2.

Healthy volunteers will be administered IP for 9 days. Blood sampling for PD assessment will be drawn on Day -1 (Period 1)/pre-dose on Day 1 (Period 2) as baseline and 24 h after dose on Day 9. Blood samples for determination of AMC will be drawn pre-dose and 0.25, 0.5, 1, 1.5, 2, 3, 4, 6, 8, 10 and 12 h after the last dose on Day 9. Safety monitoring will be performed during the treatment periods. Standardized food will be served during the residential periods. The study plan and study time schedule are found in Table 1 and Table 2, respectively.

A genetic sample will be taken to assess CYP2C19 status on Day -1 in Period 1, once the informed consent has been signed.

Table 1 Study plan

Event	Pre-entry	Perio	d 1	Period 2		Follow-up	
Study Day	within 28 days prior to randomization	Day -1 (admission)	Day 1 to 10 ^a	Day -1 (admission)	Day 1 to 10 ^a	7-10 days after the last dose	
Informed consent ^b	X						
Inclusion/exclusion criteria	X	X	X^{c}				
Randomization			X^{d}				
Demographics	X						
Body weight and height	X						
Nicotine, alcohol and caffeine use	X						
Medical and surgical history	X						
Physical examination	X					X	
Laboratory screening ^e	X	X	X^{f}	X	X^{f}	X	
Alcohol and drug screen	X	X		X			
CYP2C19 blood sample		X					
Paper ECG (pECG)	X	X		X		X	
Vital signs (BP/pulse)	X	X	X^{g}	X	X^g	X	
Administration of IP			X^h		X^h		
PK blood sampling			X^{i}		X^{i}		
PD blood sampling		X	X^{j}		X^k		
Standardized food ¹		X	X	X	X		
Concomitant medication	X	X	X	X	X	X	
AE/serious adverse event (SAE) recording ^m	X	X	X	X	X	X	

- a For treatment A, the subjects will leave the study unit after dosing on Day 1 and return in the evening on Day 8. For treatment B, the subjects will leave the study unit after dosing on Day 1 and return prior to dose on Day 5. For both treatment periods, they will be discharged from the study unit after the assessments 24 h post dose on Day 9 (ie, on Day 10).
- b If an extra pre-entry visit is needed prior to randomization, the healthy volunteers will only need to sign the informed consent once.
- c Only AEs and concomitant medication will be checked before randomization on Day 1.
- d Randomization will be done on Day 1.
- e See Section 6.3.5 for assessments. At the pre-entry visit, also including human immunodeficiency virus (HIV), hepatitis B and C.
- f On Day 9 (see Table 2)
- g Pre-dose on Days 1 and 9 (see Table 2)
- h For treatment A, administration will take place at study unit on Day 1, at home on Days 2 to 8 and at the study unit on Day 9. For treatment B, administration will take place at study unit on Day 1, at home on Days 2 to 4 and at the study unit on Days 5 to 9.
- i Pre-dose and 0.25, 0.5, 1, 1.5, 2, 3, 4, 6, 8, 10 and 12 h after the last dose on Day 9 (see Table 2)
- j 24 h post dose on Day 9 (see Table 2). The baseline sample will be obtained on Day -1.
- k Pre-dose on Day 1 (as baseline) and at 24 h post dose on Day 9 (see Table 2)
- 1 Standardized food will be served during the residential periods.
- m Serious adverse events will be collected from the time when informed consent is obtained until the follow up visit.

 Adverse events will be collected from the first administration of IP until the follow up visit.

Table 2 Study time schedule, Days 9 and 10

Protocol time (hhmm)	Study A	Administration of IP	PK blood sampling	PD blood sampling	Laboratory safety	Vital signs	Other
Pre-dose	9		X		X	X	
0000		X					
0015			X				
0030			X				
0100			X				Breakfast
0130			X				
0200			X				
0300			X				
0400			X				Lunch
0600			X				
0700							Snacks
0800			X				
1000			X				Dinner
1200			X				Snacks
2400	10			X ^a			Breakfast after PD sampling

a The baseline sample will be taken on Day -1 for Period 1 and pre-dose on Day 1 for Period 2.

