For SAEs causal relationship will also be assessed for other medication and study procedures. Note that for SAEs that could be associated with any study procedure the causal relationship is implied as 'yes'.

A guide to the interpretation of the causality question is found in Appendix B to the CSP.

Adverse events based on signs and symptoms

All AEs spontaneously reported by the healthy volunteer or reported in response to the open question from the study personnel: 'Have you had any health problems since the previous visit/you were last asked?', or revealed by observation will be collected and recorded in the CRF. When collecting AEs, the recording of diagnoses is preferred (when possible) to recording a list of signs and symptoms. However, if a diagnosis is known and there are other signs or symptoms that are not generally part of the diagnosis, the diagnosis and each sign or symptom will be recorded separately.

Adverse events based on examinations and tests

The results from protocol mandated laboratory tests and vital signs will be summarized in the clinical study report (CSR). Deterioration as compared to baseline in protocol-mandated laboratory values or vital signs should therefore only be reported as AEs if they fulfil any of the SAE criteria or are the reason for discontinuation of treatment with the IP.

If deterioration in a laboratory value/vital sign is associated with clinical signs and symptoms, the sign or symptom will be reported as an AE and the associated laboratory result/vital sign will be considered as additional information. Wherever possible the reporting investigator uses the clinical, rather than the laboratory term (eg, anaemia versus low haemoglobin value).

In the absence of clinical signs or symptoms, clinically relevant deteriorations in non-mandated parameters should be reported as AE(s).

Any new or aggravated clinically relevant abnormal medical finding at a physical examination as compared with the baseline assessment will be reported as an AE.

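### Longer unit residence in Treatment B than in Treatment A may leave mild adverse events on Days 5-8 under-recorded for clopidogrel alone

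*Protocol*

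**What the plan says.** Residence is fixed by treatment in Section 3.1 (text and Table 1, footnotes a and h) and again in Section 5.5.2. For clopidogrel alone: "For treatment A, the subjects will leave the study unit after dosing on Day 1 and return in the evening on Day 8". For clopidogrel with the combination: "For treatment B, the subjects will leave the study unit after dosing on Day 1 and return prior to dose on Day 5". Both are discharged on Day 10, after the assessments 24 h after the Day 9 dose. Section 1.3 presents the longer stay as a safety measure: "Healthy volunteers will be observed at the study unit during the treatment period when clopidogrel is administered with esomeprazole 20 mg/ASA 81 mg".

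Section 6.3.3 names three sources of AEs. It refers to "All AEs spontaneously reported by the healthy volunteer or reported in response to the open question from the study personnel", and adds events noticed by observation. The open question is "Have you had any health problems since the previous visit/you were last asked", so it looks back to the last contact.

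Table 1 marks AE recording once for the whole block of Days 1 to 10. Table 2, which covers Days 9 and 10, has no AE column. The log kept at home under Section 5.5.2 holds the date and time of each dose and nothing on symptoms.

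The second secondary objective (Section 2.2) is "To assess the safety and tolerability of clopidogrel given alone and concomitantly with esomeprazole 20 mg/ASA 81 mg". Section 12.2.4 summarizes AEs by treatment, with washout shown separately, and does not mention the difference in residence.

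**The concern.** Two of the three AE sources, the staff question and staff observation, need contact with staff. From Day 5 to the evening of Day 8 that contact is continuous in B, while the protocol schedules none in A. A short headache, mild dyspepsia or a small bruise in that time can be seen or asked about at once in B. In A it has to be volunteered, or remembered on return.

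Randomized order and within-subject comparison do not help, because each volunteer is at home on those days in A and in the unit in B, whichever comes first. The study is open-label, so blinding does not counter it either.

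At stake is how the by-treatment AE summary is read. A modest excess of mild events in B could come from the combination, from closer observation, or from both, and the data as collected could not tell these apart.

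**Working it through.** The protocol gives no figure of its own on this point, so there is none to reproduce.

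**Step 1. Unit time from the Day 5 dose to discharge.** The days come from Table 1, footnote a. The protocol gives no clock times; I assume dosing at 08:00 and an evening return between 18:00 and 22:00.

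- B: Day 5 dose to 24 h after the Day 9 dose = 5 × 24 = 120 h, or 5.0 days.
- A, return at 18:00: 6 + 24 + 8 = 38 h (1.58 days).
- A, return at 20:00: 4 + 24 + 8 = 36 h (1.5 days).
- A, return at 22:00: 2 + 24 + 8 = 34 h (1.42 days).

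The B/A ratio of unit time is 120/38 = 3.2 to 120/34 = 3.5. In A, volunteers are in the unit for 34/120 = 28% to 38/120 = 32% of that window; in B, for all of it.

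**Step 2. Unit and home time over the tabulated period.** Section 12.2.4 starts washout 24 h after the Day 9 dose, so the treatment period is 9 days from the Day 1 dose.

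- A: about 7.5 days at home and 1.5 in the unit.
- B: about 4 days at home and 5 in the unit.

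**Step 3. Illustration of size.** The protocol gives no capture rates. I assume the same constant true event rate in both treatments, 90% of events captured on unit days, and 60% or 75% on home days. Expected recorded events are proportional to (home days × home capture) + (unit days × unit capture).

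| Home capture | A | B | Apparent B/A |
|---|---|---|---|
| 60% | 7.5 × 0.60 + 1.5 × 0.90 = 5.850 | 4 × 0.60 + 5 × 0.90 = 6.900 | 1.18 |
| 75% | 7.5 × 0.75 + 1.5 × 0.90 = 6.975 | 4 × 0.75 + 5 × 0.90 = 7.500 | 1.08 |

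With no true difference between treatments, the AE summary would show 8% to 18% more events in B under these assumptions. For events starting while B is resident and A is at home, the same rates give 0.90/0.60 = 1.5 or 0.90/0.75 = 1.2, but the protocol does not plan to tabulate that subset.

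**Step 4. Which safety components are touched.** In Table 1, laboratory tests, vital signs, ECG and physical examination fall at the same points in both treatments. Of the five components in the Section 2.2 safety objective, only AEs depend on residence.

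**The case against.** The strongest reply is that the plan already covers much of the gap. Section 1.3 obliges volunteers to tell staff of any bleeding, minor or major, without limiting this to Treatment B or to unit days. Spontaneous reporting does not require residence. The open question reaches back to the last contact, so no day falls outside it, and AE collection runs from first dose to follow-up in both treatments. Safety is descriptive: no test, interval or decision rests on AE counts. Closer observation during co-administration is a deliberate safety choice.

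Most of this stands, and it limits the point. It does not remove it. An equal collection window is not equal ascertainment within the window. The bleeding duty has no stated means or timing on home days and does not cover other mild symptoms. Recall after up to about 7.5 days at home is likely to be weaker for brief events.

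It may also be said that an AE table by residence belongs in the statistical analysis plan, since AE start and stop times are recorded anyway. That holds for the table. It does not hold for collection, because an event never recorded cannot be recovered in the analysis.

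A reader might infer that the secondary safety objective as a whole is biased, or that AE counts in B would be inflated by a factor of 1.2 to 1.5. The protocol supports neither. Four of the five safety components have equal schedules, and those factors apply only to events on Days 5-8 under assumed capture rates.

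**Conclusion.** The point holds as a modest limitation on descriptive AE counts. Mild or transient AEs on Days 5-8 may be under-recorded for clopidogrel alone, and the crossover does not correct this. The residence imbalance, about 5 days against about 1.5, follows from the protocol apart from the assumed clock times. The size of the bias does not: 1.18 and 1.08 over 9 days rest on assumed capture of 90% in the unit and 60% or 75% at home, a constant event rate, and one home capture rate for both treatments. More events in B is the likely direction, not a certainty. Bleeding should be affected less than other mild symptoms if the reporting duty is followed. The primary analysis of maximal inhibition of platelet aggregation and the pharmacokinetic analyses are not touched by this point.

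**What to change.** Leave residence and in-unit observation as they are, and make the AE enquiry alike by study day.

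1. Section 5.5.2: add a dated entry for health problems and bleeding to the medication log that volunteers already keep at home, and use the same dated entry on unit days in both treatments.
2. Section 6.3.3: put the open question to volunteers in both treatments on the evening of Day 8, worded to cover Days 5-8 whenever they were last asked.
3. Section 12.2.4, or the statistical analysis plan: add a table of AEs starting from the evening of Day 8 to Day 10, when both treatments are resident, and state that AEs on Days 5-8 were collected under different observation.

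The cost is a little more recording, one common question and one extra table, and probably a few more mild AEs recorded in Treatment A. The like-for-like window is only about 1.5 days and may hold few events, so the table supplements the by-treatment summary and does not replace it. The log entry and the question must be in place before the first dose.
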